#### **4.5.7. Visit 6 (Day 50+3). Follow-up**

- registration of concomitant therapy;
- physical examination with measurement of BP, HR, and RR;
- AEs registration;
- neurological status.

Once the procedures of visit 6 have been completed, the trial will be considered complete for the patient.

After completion of all the procedures of the follow-up visit, if necessary, the investigator will prescribe treatment to the patient according to his/her judgement in accordance with current clinical practice.

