### ***6.2.3. Prohibited concomitant therapy***

The following medications are prohibited in this trial for the duration of the trial:

1. neuroprotectants, antioxidants, metabolic drugs, vasoactive and nootropic agents, including but not limited to: actovegin, Aminalon, Biotredine, Vasobral, Gliatilin, Glycine, Dimefosfon, Instenon, Cogitum, Cortexin, Cudesan, Minisem, Noben, Pantogam, Picamilon, Piracetam, Tenoten Children's, Phenibut, Cerebrolysin, Cinnarizine, Encephabol;
2. other agents affecting the central nervous system: ginkgo biloba leaf extract,

atomoxetine, tranquillisers and antidepressants.

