### ***10.2. Deviations from protocol***

In general, any deviation from the protocol may be accepted only in an urgent case or after obtaining written agreement from the Sponsor and subject to approval by the Ethics Committee. Any deviation from the protocol should be clearly explained in the source documentation and in the eCRF. Classification of protocol deviations will be made before the database cutt off by the Sponsor's medical expert. Deviations from the protocol will be considered significant in the following cases (the list may be expanded in a subsequent evaluation of protocol deviations):

- skip of visit 5;
- violation of inclusion / non-inclusion criteria;
- violation of the exclusion criteria;
- taking the Investigational product/placebo <80% or >120% of the total number of tablets prescribed;
- administration of prohibited drugs.

If significant deviations from the protocol are identified, the CRA must immediately inform the Sponsor.

In the absence of data at Visit 5 when data are available at Visit 6, these patients will not be included in the FAS and PP populations, but will be analysed in the safety population.

In the presence of data at Visit 5 and the presence of the other listed significant protocol deviations, these patients will be included in the full analysis population, safety population, but excluded from the protocol population.

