## **11. Patient populations to be analysed**

The following groups will be used for the analysis:

1. **Safety population** - will include all patients who have taken at least one dose of the investigational product;

2. **Full analysis set (FAS) population** - will include all randomized patients who have taken at least one dose of the investigational product and who have an assessed response to therapy after 6 weeks of therapy. This will be the main population for efficacy analyses;

3. **Per protocol population (PP)** is a subgroup of the FAS population that will include patients in the absence of significant protocol deviations regarding inclusion/non-inclusion criteria, adherence to therapy, and use of concomitant therapy. This will be an additional population used for efficacy analyses.

Efficacy analyses will be performed on the FAS population as well as on the PP population of all patients who completed the trial according to the protocol in order to validate the results obtained.

The final Clinical Trial Report will include data on all patients included in the trial, including those who dropped out at any time without explanation.

In general, any deviation from the protocol may be accepted only in an urgent case or after obtaining written agreement from the Sponsor and subject to approval by the Ethics Committee. Any deviation from the protocol should be clearly explained in the source documentation and in the eCRF. Classification of protocol deviations will be made by the Sponsor's medical expert before the database lock. Deviations from the protocol will be considered significant in the following cases (the list may be expanded in a subsequent evaluation of protocol deviations):

- skip of visit 4;
- violation of inclusion / non-inclusion criteria;
- violation of the exclusion criteria;
- taking the investigational product/placebo <80% or >120% of the total number of tablets prescribed;
- administration of prohibited drugs.

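### A prohibited drug started after the Day 43 primary score still removes the child from the per-protocol set, so PP membership can depend on the outcome

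*Protocol*

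**What the plan says.** **Timing.** Protocol 4.5.6 puts the last SNAP-IV assessment at Visit 5, Day 43+1. Visit 6 (Day 50+3) has no efficacy scale, but its procedures include "registration of concomitant therapy". Section 4.5.7 then states: "Once the procedures of visit 6 have been completed, the trial will be considered complete for the patient".

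**The ban.** Protocol 6.2.3 opens its list with: "The following medications are prohibited in this trial for the duration of the trial".

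**The consequence.** Protocol 10.2 and SAP 11 both list "administration of prohibited drugs" among the significant deviations, without a period. For a child who has end-of-therapy data and one of the other listed deviations, 10.2 says that "these patients will be included in the full analysis population, safety population, but excluded from the protocol population". SAP 11 repeats the rule under different visit numbers.

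**What PP is.** The formal definition in SAP 11 (and in Protocol 9.7) makes PP a "subgroup of the FAS population that will include patients in the absence of significant protocol deviations". Shortly afterwards SAP 11 describes it as the "PP population of all patients who completed the trial according to the protocol in order to validate the results obtained". SAP 6 uses PP as a sensitivity analysis of the primary variable; FAS is the main population.

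**The concern.** A deviation normally matters to a per-protocol analysis because it could have altered the measurement. A drug first taken on Day 45 cannot alter a score recorded on Day 43. Influence can run the other way: a child who did poorly at Day 43 is a more likely candidate for another treatment. Excluding that child selects the PP set on the very outcome being analysed.

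At stake is how the FAS and PP results are read together. The SAP looks to PP for consistency with the main analysis. If membership depends on events after the endpoint, a gap between the two analyses, or agreement between them, could partly be a product of the rule and say little about adherence to the protocol.

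**Working it through.** **1. The rule, followed step by step for one child**

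- Day 43: valid SNAP-IV score; no deviation so far.
- Day 45: starts a drug on the 6.2.3 list. The ban still applies, because by 4.5.7 the trial ends for the child only after Visit 6.
- Visit 6: concomitant therapy is recorded. Protocol 6.2.2 requires start and discontinuation dates, so the use is captured and dated.
- Classification: the use is a listed significant deviation. Both documents say that the list may be expanded; neither says that an item may be waived by timing.
- Result: in FAS and safety, out of PP.

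**2. Length of the exposed window**

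With the section 4.5 windows, Visit 5 falls on Day 43 to 44 and Visit 6 on Day 50 to 53. The gap is 50 - 44 = 6 days to 53 - 43 = 10 days. The schedule in Protocol 1.2 prints 43±1 and 50±3, which would give 47 - 44 = 3 to 53 - 42 = 11 days.

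**3. The plan's own figures**

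Inputs from Protocol 9.2: change of -2.0 (SD 4.70) on placebo and -4.5 (SD 7.515) on Mexidol; two-sided alpha 0.05; power 80%.

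- Difference: -4.5 - (-2.0) = -2.5.
- Pooled SD: √((4.70² + 7.515²)/2) = 6.27.
- n per group = 2 × 6.27² × (1.960 + 0.842)² / 2.5² = 99 by the normal formula, and 100 by the noncentral t (power 80.1%). The stated 100 per group reproduces.

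**4. If removal is unrelated to outcome**

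Losing 1, 2 or 5 of 100 scores in each arm takes t-test power from 80.1% to 79.7%, 79.3% or 78.1%. This is minor.

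**5. If removal is linked to outcome**

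Assume normal changes and that the removed children are exactly the worst fraction q of an arm. With z the upper-q normal quantile and φ the normal density, the arm mean shifts towards improvement by SD × φ(z)/(1 - q).

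Example for q = 5%: φ(1.645)/0.95 = 0.1086. The placebo shift is 4.70 × 0.1086 = 0.51, and the active shift is 7.515 × 0.1086 = 0.82. Removal from placebo only gives -2.5 + 0.51 = -1.99. Removal from both arms gives -2.5 - 0.82 + 0.51 = -2.81.

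| Worst fraction removed | Placebo only | Both arms |
|---|---|---|
| none | -2.50 | -2.50 |
| 1% | -2.37 | -2.58 |
| 2% | -2.27 | -2.64 |
| 5% | -1.99 | -2.81 |

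The two columns move in opposite directions, so the sign of any distortion depends on which children leave and from which arm. The documents give no rate of drug use during follow-up; every fraction here is an assumption.

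**The case against.** **Only a supportive analysis is touched.** This is correct. FAS keeps every such score. SAP 6 also plans a site-adjusted model, supporting secondary endpoints, and complete-case and last-observation-carried-forward analyses, so PP is one check among several.

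**Exposure is small.** This also largely stands. Section 4.5.7 places further treatment by the investigator after the Visit 6 procedures, so a start on Day 45 would itself breach the protocol. Exclusion criteria and adherence are last assessed at Visit 5. Deviations are classified before database lock and the codes are opened afterwards (Protocol 10.2 and 4.9), so the classification cannot be steered by arm. That last safeguard does not prevent outcome-linked selection, because the rule operates without anyone knowing the arm.

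**The illustration is a worst case.** Agreed. It assumes a perfect link between a poor score and removal.

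**A reader might infer that a missed Visit 6 also removes a child from PP**, by joining the SAP 11 phrase about completing the trial to section 4.5.7. The documents do not support that as a rule. The formal PP definition has no Visit 6 condition. The only missed visit on either list is the end-of-therapy one: Visit 5 in Protocol 10.2, and Visit 4 in SAP 11, where SAP Table 2 labels Day 43+1 as Visit 4. The phrase is loose wording to be aligned with the definition.

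**Conclusion.** As written, the prohibited-drug rule lets an event after the endpoint discard a valid Day 43+1 score from PP. This follows directly from Protocol 4.5.7, 6.2.3 and 10.2 and SAP 11.

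Its reach is limited to the PP sensitivity analysis and probably to few children. Size and direction are unknown. Under the assumptions above, losing the worst 1% to 5% of placebo scores only would move the planned -2.5 to about -2.4 to -2.0, and losing the worst 5% of both arms would move it to about -2.8.

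It would be wrong to conclude that the primary analysis is biased, or that a material PP distortion should be expected. The first is excluded by the FAS rule, and the second has no rate in the documents behind it. The point is worth acting on because the better rule costs almost nothing and is harder to defend if introduced after unblinding.

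**What to change.** Before unblinding, in Protocol 10.2 and SAP 11:

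- Count deviations for PP only from randomisation up to completion of the end-of-therapy (Day 43+1) SNAP-IV assessment. Eligibility violations continue to count as now.
- Define that cut-off by day, not by visit number. In SAP 11 and SAP Table 2, Day 43+1 is Visit 4 and Day 50+3 is Visit 5, whereas SAP Table 3 and Protocol version 4.0 call Day 43+1 Visit 5. Writing a Visit 5 cut-off into SAP 11 under that section's own numbering would extend it to the follow-up visit.
- Use the formal PP definition throughout SAP 11 in place of the phrase about completing the trial.
- Reconcile the SAP's visit labels with Protocol version 4.0; the SAP was written for version 3.0, and Visit 4 is now the Day 28 telephone contact.

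The drug ban itself is not in question here and stays as it is. Later use remains a recorded deviation in the listings.

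Cost: one sentence on the cut-off in each document, plus the alignment of wording and visit numbers in the SAP. No new data are needed, because drug start dates are already collected, and no sample-size figure changes.

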#### **4.5.8. Unscheduled visits**

Additional unscheduled visits may be made if necessary (e.g., in the case of AEs/SAEs). In this case, detailed information about the visit (reason for visit, examination results) is entered on the relevant pages of the eCRF "Unscheduled visit".

#### **4.5.9. Examination in case of early termination**

If a patient is early withdrawn from the trial or parents withdraw consent for the patient to participate in the trial after the start of investigational product administration, the patient will be asked to return to the site for a final safety assessment to ensure the patient's well-being. The procedure for this examination is identical to the procedures at Visit 5.

#### **4.5.10. Completion of the trial**

The investigational site must fully complete the trial and complete all required documentation in full compliance with the protocol. The trial may be suspended by either the Sponsor or the investigational site until completion of the trial if objective reasons arise. Notices of suspension should be sent to all parties involved in the trial as soon as possible. Any increase in the trial timeline must be agreed between the Sponsor and the investigational site and documented.

Notification of the completion of the trial must be sent to the authorised federal authorities within 5 working days.

### **4.6. Description of the trial procedures**

#### **4.6.1. Collection of demographic data and anamnesis, anthropometry**

At the Screening Visit, after signing the informed consent form, the following data will be

collected from all patients:

- Gender, age (date of birth).
- Detailed medical history (*anamnesis vitae et anamnesis morbi*), including:
  - previous injuries and surgeries (dates, indications, extent of surgical intervention);
  - past illnesses;
  - allergological history;
  - medicines used in the previous 30 days or 5 half-lives (whichever is longer) prior to the screening visit and currently used medicines, as well as herbal medicines and nutritional supplements.

#### **4.6.2. Physical examination**

Physical examination will be performed at the screening visit (Visit 1), Visits 5 and 6 to ascertain normal and altered patient physical findings prior to administration of investigational products and to identify possible changes after administration. Acceptable examination turnaround times are shown in Table 1.2.

The physical examination includes assessment of:

- general condition;
- skin conditions;
- musculoskeletal system;
- lymph nodes;
- thyroid gland;
- upper respiratory tract and lungs;
- heart, the blood vessels;
- abdominal organs, kidneys;
- neuropsychiatric status.

#### **4.6.3. Vital signs**

Measurement of vital signs of body activity will be performed at each visit (except for the randomization visit). Allowable time periods are shown in Table 1.2.

The assessment includes:

- systolic and diastolic blood pressure (BP);
- pulse rate per 1 minute;
- respiratory movements per 1 minute

BP and pulse rate measurements are taken on the same arm in a seated or semi-recumbent position, after 5 minutes of rest and, if possible, by the same investigational site team member during a particular patient's participation in the trial.

#### **4.6.4. Neurological status**

Neurological status will be assessed at the screening visit to see if there are changes in

neuropsychiatric status prior to administration of Investigational products, and at visits 5 and 6 to see if there are possible changes after administration. Acceptable examination turnaround times are shown in Table 1.2. Neurological status includes assessment of general symptomatology and history, general cerebral and focal symptoms, assessment of motor functions, assessment of sensory sphere, reflexes, assessment of other systems and organs (including memory functions, intellectual level, emotional state).

#### **4.6.5. Anthropometry**

Anthropometry involves measuring:

- height (without shoes), the value obtained is recorded by rounding to the nearest integer value in centimetres.
- body weight (without street clothes and shoes), the value obtained is recorded by rounding to the nearest tenth of a kilogram.

Body mass index is calculated using the formula weight / (height, m) (kg/m^2).

#### **4.6.6. Patient diary**

The patient diary is issued at Visit 2 after randomization. In the Diary, the patient/patient's parents should record the dates and times of drug administration, any adverse events that occurred during treatment, if any, and all concomitant medications (both those first prescribed during the trial and dosage changes to previously prescribed medications, including withdrawals). The patient diary is returned at Visit 5. The investigator should check the quality and completeness of the completion of the Patient Diary.

#### **4.6.7. Completion of questionnaires**

The SNAP-IV, SCAS, ADHD Rating Scale IV questionnaires, child/adolescent headache examination charts, and PedMIDAS questionnaires are completed by the investigator from the patient's parents at the trial visits (Table 1.2). The questionnaires should be assessed by the same parent throughout the trial. The Child/Adolescent Headache Assessment Card and PedMIDAS questionnaire are completed only if the patient has headache complaints identified at Visit 2; scale data are completed at Visit 2 for the past 3 months, at Visit 5 for the past 1.5 months (6 weeks).

The CGI-ADHD-S, CGI-I scales are assessed by the investigator. These scales are scored and completed by the same researcher who made the original measurements.

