 If the patient has headache complaints, at Visit 2, to be completed for the previous 3 months; if the patient has headache complaints identified at Visit 2, to be completed at Visit 5, to be completed for the last 1.5 months (6 weeks)

Procedures	Screening	Initiation of therapy	Visits			Follow-up
			Telephone contact 	Telephone contact 	Therapy	
Day	-14-1	1	14±2	28±2	End of therapy	50±3
Visit number	1	2	3	4	5	6
Issuance of the Patient Diary and instructions on how to complete it		X				
Collecting the Patient Diary and monitoring its completion					X	

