**17.8. PedMIDAS questionnaire (to be completed only if the child has a headache)**

(Visit 2 is filled out for the last 3 months, Visit 5 is filled out for the last 1.5 months (6 weeks))

Completion date \_\_\_\_\_

**Surname and  
first name** \_\_\_\_\_

[figure not shown]
[figure not shown]
**Please answer each question about how your life has been affected by the headaches you have had in the past three (1.5) months**

The number of days on which there was some difficulty due to headache should be entered in the box.

If there were no difficulties, 0 days are indicated.

If the number of days is difficult to be exact, count them roughly but most reliably.

1	How many school days have been completely missed at school (institution) due to headaches in the last 3 (1.5) months?	 days
2	How many school days were partially missed at school (institution) due to headaches in the last 3 (1.5) months? (not including completely missed days in the answer to question 1)	 days
3	How many days in the last three (1.5) months have you done less than half-heartedly at school because of a headache? (not including the days listed in the answers to questions 1 and 2)	 days
4	How many days in the last three (1.5) months have you been unable to do things at home (e.g., daily chores, homework, etc.) because of a headache?	 days
5	How many days in the last three (1.5) months have you been unable to participate in other activities (e.g., participate in games, walks, sports) because of a headache?	 days
6	How many days in the last three (1.5) months were you able to participate in these activities but did less than half-heartedly? (not including the days listed in the answer to question 5)	 days
TOTAL		 days

A	How many days in the last three (1.5) months have you had a headache? (If the headache lasted more than one day, all days are counted)	 days
B	On a scale of 0 to 10 (put a vertical line), rate how much on average the headaches have been severe over the past 3 (1.5) months. 	
C	Rate on a scale of 0 to 10 points (put a vertical line) worst headaches you have had in the last three (1.5) months. How many times have it happened? _____ How long did it last? _____ 	

[ ] unbearable [ ]

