## Plan for statistical analysis of efficacy and safety parameters

Table 4. Statistical analysis of secondary, endpoints (SNAP-GU, CGI-ADHD-S, SCAS, PedMIDAS and ADHD Rating Scale IV) (template)

Indicator 	Mexidol®				Placebo				Mexidol®+ Placebo			
	Visit 2 (Day 1)	Visit 5 (Day 43+1)	Dynamics		Visit 2 (Day 1)	Visit 5 (Day 43+1)	Dynamics		Visit 2 (Day 1)	Visit 5 (Day 43+1)	Dynamics	
			Abs.	%			Abs.	%			Abs.	%
N												
Mean												
95% CI, L												
95% CI, U												
Median												
Min												
Max												
Q 1												
Q 3												
Range												
QRange												
SD												
CV												
Intragroup comparison: comparison of data at the end of therapy with data at the start of therapy (statistical criterion  ) (p-level value)												
Comparison of drugs (statistical test  ) (p-value)												
Indicator span diagram/ indicator scatter diagram												

 - SNAP-IV subscale score - "inattention."

- SNAP-IV subscale score - "hyperactivity/impulsivity."

- SNAP-IV subscale score - oppositional defiant disorder;

- SNAP-IV subscale score - Conners index;

Clinical Global Impressions-ADHD-Severity scale (CGI-ADHD-S).

- Spence children's anxiety scale (SCAS) scores after 6 weeks of therapy compared to baseline;

PedMIDAS questionnaire score

- ADHD Rating Scale-IV score after 6 weeks of therapy compared with baseline.

 T-test for related samples or Wilcoxon test depending on the type of distribution of the indicator T-test for independent samples or Mann-Whitney test depending on the type of distribution of the indicator**Version 1.0 of 27.9.2019**Protocol-specific version for protocol #PHS-ADHD-002-MEX- TAB,  
version 3.0 dated 19.07.2019.**CONFIDENTIAL**

page 33 of 42

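### PedMIDAS day counts cover 3 months at Visit 2 and 6 weeks at Visit 5 with no common period, so the planned within-arm change is about -50% when nothing has changed

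*Protocol*

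**What the plan says.** Secondary criterion 8 (Protocol 4.1 and 7.1; repeated in SAP 1 and 6) assesses the change in four PedMIDAS quantities: days with restricted activity, days with headache, average severity and maximum severity.

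- **Windows.** Protocol 4.6.7 states: "scale data are completed at Visit 2 for the past 3 months, at Visit 5 for the past 1.5 months (6 weeks". Sections 4.5.3 and 4.5.6 repeat this, and the Visit 5 part of the Schedule footnote in 1.2 reads "to be completed for the last 1.5 months (6 weeks". The form is completed only for children whose headache complaints were identified at Visit 2.
- **Items.** Protocol 17.8 asks for a number of days over the whole window. Item A is "How many days in the last three (1.5) months have you had a headache". Item 1 of the restriction total is "How many school days have been completely missed at school (institution) due to headaches in the last 3 (1.5) months".
- **Analysis.** SAP section 12, Table 4 lists a "PedMIDAS questionnaire score" among its indicators. It sets Visit 2 beside Visit 5, gives absolute and percentage change, and has a within-arm row (paired t-test or Wilcoxon) and a between-arm row (t-test or Mann-Whitney).
- **Conversion.** There is none in either document. The data-harmonisation rule in SAP 10 concerns units of measurement, and both counts are already in days.

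**The concern.** A count over 6 weeks is compared directly with a count over a window twice as long. A child whose headaches have not changed will appear to have about half as many. The within-arm change, percentage change and p-value for these counts then measure mainly the ratio of the windows, in all three arms.

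SAP 2 says the results will go into the registration dossier and publications. A row showing headache days halved with a small p-value could be misread there as a headache benefit. There is also a possible cost to the comparison with placebo, which is the stated objective in Protocol 3.2: on raw absolute change, each child's own headache frequency does not cancel and enters as noise.

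**Working it through.** The documents give no PedMIDAS figure to reproduce.

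**1. Expected change with no true change**

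Inputs: windows of 3 months and 1.5 months = 6 weeks (Protocol 4.6.7). Formula: Visit 5 window / Visit 2 window - 1.

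- By the protocol's own labels: 1.5/3 - 1 = -50.0%. Equivalently, if 1.5 months is 6 weeks then 3 months is 12 weeks, and 42/84 - 1 = -50.0%.
- If 3 months is taken as calendar days: 42/91 - 1 = -53.8%; 42/92 - 1 = -54.3%.

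This step needs no assumption about headache rates.

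**2. Within-arm test with no true change (illustrative)**

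The documents give neither headache frequency nor the number of children with headache. Two sets of assumptions were simulated. Neither excludes children with no headache day at Visit 2.

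- Windows of 91 and 42 days, 15 to 60 headache children per arm, 2 to 8 headache days per month: the raw Wilcoxon test gave p<0.05 in 96 to 100% of trials, against 4 to 6% after rescaling.
- Windows in the ratio 12:6 weeks, 8 children per arm, mean 6 / 12 headache days per 12 weeks: the raw paired t-test rejected in 49% / 72%.

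**3. Between-arm power on absolute change (illustrative)**

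Assumptions: headache days Poisson; child-specific rate L per 12 weeks, gamma with shape 1.5 and mean 6, so var(L) = 36/1.5 = 24; true 50% reduction in the treated arm; 30 children per arm; two-sided 5%.

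*Raw change (Visit 5 count - Visit 2 count)*
- Expected change: control 0.5L - L = -0.5L; treated 0.25L - L = -0.75L. Mean difference: 0.25 x 6 = 1.5 days.
- Variance, control: 0.25 x 24 + 6 + 3 = 15. Treated: 0.5625 x 24 + 6 + 1.5 = 21.
- SE = sqrt((15 + 21)/30) = 1.095; 1.5/1.095 = 1.37; power about 28%.

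*Converted change (2 x Visit 5 count - Visit 2 count; the same test as on a 28-day scale)*
- Expected change: control 0; treated -0.5L. Mean difference: 3 days.
- Variance, control: 6 + 4 x 3 = 18. Treated: 0.25 x 24 + 6 + 4 x 1.5 = 18.
- SE = sqrt(36/30) = 1.095; 3/1.095 = 2.74; power about 78%.

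Simulation of this model gives 27% raw and 79% converted. Limiting it to children with at least one Visit 2 headache day, which is closer to the form's intended population, gives for t-tests:

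| Quantity compared between arms | Mean 6 days per 12 weeks | Mean 12 |
|---|---|---|
| Raw absolute change | 31% | 36% |
| % change | 66% | 84% |
| Visit 5 count alone | 73% | 80% |
| Converted absolute change | 83% | 97% |

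With no true difference, the between-arm test on absolute change rejects in about 5% of simulated trials, raw or converted.

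**4. Residual error of the conversion**

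Per 28 days: 84/28 = 3, so Visit 2 count / 3; 28/42 = 2/3, so Visit 5 count x 2/3. If parents actually recall 91 days at Visit 2, dividing by 3 leaves 84/91 - 1 = -7.7%. If they recall 84 days and 28/91 is used, 91/84 - 1 = +8.3% is left. Both are small beside -50%.

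**The case against.** **The artefact is common to all arms and decides nothing.** This stands. The objective is comparison with placebo, no conclusion rule uses the within-arm row, and the ratio is the same by design for every child. A reader might infer that unequal windows could create a false advantage over placebo. The documents do not support that: the expected shift is equal across randomised arms and the between-arm type I error is kept.

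**The power loss depends on a choice the SAP leaves open.** This also stands. Table 4 does not say whether its between-arm row tests the absolute change, the percentage change or the Visit 5 value. The last two are not biased by the window ratio, and against them conversion gains much less. With 8 to 10 headache children per arm and mean 6, power on absolute change is only 10 to 12% raw and 28 to 35% converted. A general loss of power cannot be claimed.

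**Table 4 names one PedMIDAS score, while criterion 8 names four quantities.** True. The point assumes that the template is applied to the day counts, which is the natural reading. The power figures are for headache days only.

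**The SAP was written for protocol 3.0, and the protocol supplied is 4.0.** The windows in version 3.0 cannot be seen. Neither document supplied contains a conversion.

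**The severity items.** A reader might infer that average and worst severity also shift, because more children will have no headache in the shorter window and the form's zero rule, "If there were no difficulties, 0 days are indicated", covers days only. The documents do not establish this. The severity scales are figures not reproduced in the text, their lower anchor is not visible, any shift depends on an unknown recording practice, and Protocol 9.5 already says missing data are not replaced.

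**Conclusion.** The point holds for the two day counts. As planned, their within-arm change is expected to be -50% (about -54% on calendar days) in every arm with no change in headache frequency, and the within-arm p-value is invalid as a test of change in frequency. That rests only on the protocol's stated windows and the absence of a conversion.

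The effect on the comparison with placebo is conditional. Type I error is kept. Power falls if raw absolute change is tested, from 83% / 97% to 31% / 36% at mean 6 / 12 headache days per 12 weeks. Those figures rest on an assumed headache rate, an assumed 30 headache children per arm and an assumed 50% reduction, and show direction and rough size only.

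The primary endpoint, the superiority rule and the sample size are untouched. This is a minor correction to one of nine secondary criteria, in the subgroup with headache.

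**What to change.** Add a paragraph to the SAP, before any change, percentage change or test is computed:

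- Express both PedMIDAS day counts per 28 days: Visit 2 count / 3 and Visit 5 count x 2/3, following the protocol's 12:6-week ratio.
- As a sensitivity choice, use Visit 2 count x 28/91.
- Note that the scaling is approximate for restriction items 1 to 3, which concern school days, because the two windows need not contain school days in the same proportion.

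The cost is a short SAP text change on data already collected. The form, the visits and the 6-week window, which matches the treatment period, can stay as they are. Protocol 9.6 has the SAP approved before database cut-off, so the rule can be fixed in advance.
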